**Secondary:**

- AE monitoring will occur both actively and passively. All AE will be graded and analyzed by seriousness, intensity and causality. AE monitoring in this study is crucial to properly weigh the potential benefits vs. potential risks of the study.

In the entire enrolled populace, passive monitoring of AEs will occur through spontaneous reporting of adverse events to the study clinical team and recorded on CRFs. Active monitoring of AEs will occur among participants in two ways, a) on the days of distribution of ivermectin/placebo through direct questioning of participants for AEs and recording on CRFs by study nurses and, b) in a weekly visit and assessment of participants living in selected households located on our entomological sampling transects. AEs will be recorded from the entire enrolled populace, regardless if they were treated with ivermectin/placebo or not eligible to take the intervention. AE will be recorded over the intervention period occurring during the 1st and 2nd rainy seasons. More

specifically, AEs will be recorded from the start of the first MDA of each rainy season to 1 month after the last MDA of that season.

For those children enrolled in the active case detection cohort, where children are visited weekly to assess for malaria incidence, active monitoring of AEs will occur through direct questioning of AEs by the study team. Additionally, passive monitoring of AEs will occur by participants spontaneously reporting directly to the nurses when the nurses are in the villages performing active case detection of malaria in the child cohort, or spontaneously reporting indirectly to the nurses via communication through the village community health worker (who will then communicate the AE directly to the nurse or field physician).

For women that become pregnant during the intervention period, monitoring for birth outcomes will be conducted.

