**Table 3: Summary of the study groups and schedule for blood sampling.**

Group	Number to sample	Ages	What and when samples collected				
			BS=blood smear FP=filter paper	BS&FP -when malaria diagnosed	BS&FP -before season	BS&FP -between the second and third MDA each season	BS&FP -dry season/ post intervention (only from select participants)
Child cohort (followed with active case surveillance)	~1800	≤10 yr. olds	BS&FP -when malaria diagnosed	BS&FP -before season	BS&FP -between the second and third MDA each season	BS&FP -post season	BS&FP -dry season/ post intervention (only from select participants)
Households# on village transects (3 villages/arm; ~8 households/village)	~380	all note: ≤10 yr. olds will be sampled in the ACD cohort		BS&FP -before season	BS&FP -between the second and third MDA each season	BS&FP -post season	BS&FP -dry season/ post intervention
PK-PD modeling cohort	180	5-10yo (n=30 per arm) 11-18yo (n=30 per arm) ≥19yo (n=30 per arm)	Each participant sampled for capillary blood up to 5 of the following time points after their last dose of IVM: 0h (pre-last dose), 1h, 4h*, 8h, 12h*, 24h, 48h, 52h, 60h, 72h, 7d*, 14d, 21d and 28d. *venous blood will be collected simultaneously at these time points				

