occur around between the 2nd and 3rd MDA round due to the time it will take to input and collate data. At the time of this review, and all others, it is recommended that if treatment-related AEs (Grade 2 or above) occur in 10% of the treated participants in the intervention arm, or if treatment-related SAE occur in 2% of the treated participants in the intervention arm, the following will take place:

- The dose of IVM will be reduced to a 1x400 µg/kg dose (see section 6.3).
- The DSMB should immediately convene an ad-hoc meeting that considers both unblinded safety data, as well as efficacy data (modeled and actual effect size of the primary outcome), to consider whether the study should be halted early or continue with a 1x400 µg/kg dose.

The DSMB will have a scheduled meeting between the 2nd and 3rd MDA round, and after the completion of 1st rainy season. At this point, the DSMB will review all safety data to determine if dose modification is potentially warranted.

Following recommendation from the DSMB, the sponsor reserves the right to temporarily suspend or prematurely discontinue this study at any time for reasons including, but not limited to, safety or ethical issues or severe non-compliance. If the sponsor determines such action is needed, it will discuss this with the investigators. When feasible, the sponsor will provide advance notification to the investigator of the impending action prior to it taking effect. The sponsor will promptly inform the DMID/NIH, the CSU and Yale IRBs and the Comité d’Ethique of the IRSS, and provide the reason for the suspension or termination. The study may also be suspended or terminated at the discretion of the DMID/NIH based on funding decisions.

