## 10. STATISTICAL CONSIDERATIONS

### 10.1. Study Hypotheses

The primary objective hypothesis is that repeated IVM MDAs (the intervention) coinciding with SMC rounds and other standard-of-care malaria control measures (LLIN distribution, IPTp) will significantly reduce the incidence of childhood malaria compared to the placebo intervention. This hypothesis will be tested in a 2-arm superiority trial with a cluster randomized design. The primary outcome measures of incidence of malaria episodes among village children ≤ 10 years of age in each arm will be used to test the hypothesis. The primary objective null hypothesis is that that repeated IVM MDAs coinciding with SMC rounds and other standard-of-care malaria control measures will have no effect on the incidence of childhood malaria compared to placebo MDAs coinciding with SMC rounds and other standard-of-care malaria control measures.

Secondary objective hypotheses:

- The risk of adverse events (AEs) per participant in the intervention arm occurring over the intervention phase of the trial will not differ relative to the risk of adverse events in the control arm.  
*Null: The risk of adverse events (AEs) per participant in the intervention arm occurring over the intervention phase of the trial will not differ relative to the risk of adverse events in the control arm.*
- The survival rates of wild blood fed *Anopheles gambiae* s.l. will be significantly reduced, and age-structure and entomological inoculation rate in wild *Anopheles gambiae* s.l. significantly younger/lower, in those captured from intervention arm villages as compared to those captured control arm villages at equivalent time intervals during the intervention phase. Also, the immuno-reactivity of intervention-arm participants' IgG over time to an *Anopheles* salivary gland peptide will be significantly lower than that from control arm participants.  
*Null: The survival rates of wild blood fed Anopheles gambiae s.l., and parity and sporozoite rates in wild Anopheles gambiae s.l., will not differ in those captured from intervention arm villages as compared to those captured control arm villages at equivalent time intervals during the intervention phase. Similarly, the immuno-reactivity of intervention-arm participants' IgG over time to an Anopheles salivary gland peptide will be no different than that from control arm participants.*

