2.1.2 Definition of primary efficacy endpoint

A malaria episode is defined as the presence of a temperature of ≥37·5°C and/or history of fever in the last 24 hours, along with a positive rapid diagnostic test (RDT) for *Plasmodium* species (any species).

A participant's time-at-risk will be considered as censored for 14 days following a diagnosis and treatment of malaria due to the impacts of treatment on risk of recurrent malaria. Person time will be defined in 7-day consecutive intervals, with one or more visits occurring during this time considered as an eligible person-week.

Eligibility for MDA is determined at the beginning of each intervention season and is retained for the remainder of that season.

- Newborns are eligible for inclusion and will be considered exposed beginning at the time of their 1st ACD visit.
- Children who turn 11 years of age during an intervention season will remain eligible for the ACD cohort for the remainder of that season.
- If a participant ages out of ACD cohort in the first season, they will not be eligible for the ACD cohort in the second season.
- Eligibility for SMC is determined by the MoH community workers, not by the RIMDAMAL II study team. Participants may age out of SMC (>59 months) in the 1st season and become eligible for MDA (≥90 cm and >59 months) in the second season. They will not become eligible for MDA during the season where this occurred.

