2.2 Secondary endpoints

- **2.2.1** Adverse events analysis: Safety is a secondary endpoint and will be assessed by relative risk (RR).
 - a. Groups
 - All participants_will be followed actively and passively for adverse events and the Risk Ratios (RR) of AEs in those in the intervention versus control clusters will be compared.
 - ii. Active Case Detection Cohort

- SMC-treated children only children age 3-59 months who receive SMC. RR of AEs in children who receive SMC and live in IVM-treated clusters versus those who receive SMC and live in placebo-treated clusters
- 2. **IVM/placebo-treated only** children ≥90cm and eligible for MDA/placebo. RR of AEs in those children receiving MDA versus those receiving placebo.
- iii. **Non-ACD participants** that were enrolled in the study were actively followed in the study on the days of study intervention through 24-hours post study intervention, and then passively for the rest of the MDA round.
- b. **Type** AEs will be further classified by seriousness, severity, relationship to the intervention, outcome, and organ system.
 - i. Classification (AE, SAE, etc)

Adverse Event: (ICH) E6 defines an AE as any untoward medical occurrence in a patient or clinical investigation subject administered a pharmaceutical product regardless of its causal relationship to the study treatment. FDA defines an AE as any untoward medical occurrence associated with the use of a drug in humans, whether or not considered drug related. An AE can therefore be any unfavorable and unintended sign (including an abnormal laboratory finding), symptom, or disease temporally associated with the use of a medicinal product.

Serious AE (SAE): An AE is considered "serious" if, in the view of either the site principal investigator or sponsor, it results in any of the following outcomes:

- 1. Death.
- 2. A life-threatening AE: An AE is considered "life-threatening" if, in the view of either the site principal investigator or sponsor, its occurrence places the patient or subject at immediate risk of death. It does not include an AE that, had it occurred in a more severe form, might have caused death.
- 3. Inpatient hospitalization or prolongation of existing hospitalization.
- 4. A persistent or significant incapacity or substantial disruption of the ability to conduct normal life functions, or
- 5. A congenital anomaly/birth defect.

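### Outside the child cohort the SAP specifies no adverse-event risk ratio among people who took the tablets, and the all-enrolled ratio is diluted for all-cause events

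*SAP*

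**What the plan says.** SAP 2.2.1 opens by saying that safety is assessed by relative risk, then lists groups.

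- Group i is all participants, by cluster arm: "Risk Ratios (RR) of AEs in those in the intervention versus control clusters will be compared". SAP 2.1.1 and protocol 3.2.2 and 8.3 make clear that this deliberately includes people who were not treated or not eligible.
- Group ii.1 is cohort children on seasonal malaria chemoprevention (SMC), by cluster arm.
- Group ii.2 is cohort children eligible for the tablets: "RR of AEs in those children receiving MDA versus those receiving placebo".
- Group iii is participants outside the active case detection (ACD) cohort. The entry describes active follow-up to 24 hours after the intervention, "and then passively for the rest of the MDA round". It names no comparison and is not limited to dosed people.

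The hypothesis in protocol 10.1 is framed per participant: "The risk of adverse events (AEs) per participant in the intervention arm occurring over the intervention phase of the trial". SAP 2.1 and protocol 4 and 10.3.1 compare AEs by arm without defining a dosed set.

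Three other provisions touch on dosed people:

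- The guideline in protocol 8.4 is triggered if treatment-related AEs of grade 2 or above "occur in 10% of the treated participants in the intervention arm". This is a percentage in one arm.
- Planned Figure S3.1 is a flow diagram.
- The PK/PD cohort has 60 people over 10 per arm, and the SAP appendix lists its safety analysis as future work.

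**The concern.** Group ii.2 answers the question a person offered the tablets would ask: how much does taking them raise my risk of an adverse event, compared with taking placebo? The SAP answers it for children up to 10 and stops there, although most dosed people are older. Protocol 2.3.1 names more frequent dosing, of more people and over a wider age range, as the trial's greatest potential risk.

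For older dosed people the stated figure is the all-enrolled ratio, in which undosed people contribute events that the drug did not cause. For a harm estimate, that pull towards no difference is the unfavourable direction. Protocol 8.4 already recognises the distinction: it reports the pilot's AEs over all arm participants (45 in 1447) and then related AEs over treated participants (5 of 787).

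**Working it through.** The plan gives no figure of its own to reproduce here. The check is which comparisons are specified (above) and how much the pooled ones could dilute an effect.

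**Inputs, per arm.** The Treatment Arms table in the Protocol Summary gives about 2500 participants, about 75% dosed, and more than 700 cohort children (700 used). So 0.75 × 2500 = 1875 are dosed, 625 are not, and 2500 − 700 = 1800 are outside the cohort.

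**Assumptions.** The documents give no age breakdown. I spread the cohort evenly over the eleven single years 0 to 10, so 700 × 6/11 = 382 are aged 5–10 and 318 are under 5. The range shown is 40% to 65% of the cohort aged 5–10 (280 to 455 children). All cohort children aged 5–10 are taken as dosed.

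**1. Dosed people outside group ii.2.** 1875 − 382 = 1493, and 1493/1875 = 80%. Range: 1595/1875 = 85% to 1420/1875 = 76%.

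**2. Dilution in group i, all-cause events.** With dosed share d, true ratio R in the dosed, ratio 1 in the undosed and equal background risk:

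pooled RR = 1 + (R − 1) × d

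At d = 0.75, R = 2.0 shows as 1.75 and R = 1.5 as 1.375.

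**3. Ever-dosed ceiling.** The table does not say whether 75% is per round or over the trial. Suppose everyone outside the cohort is dosed at least once in eight rounds. Children on SMC are not dosed, and for those who pass 59 months mid-season SAP 2.1.2 says: "They will not become eligible for MDA during the season where this occurred". About one fifth of the under-fives (318/5 = 64) can therefore enter in season 2.

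- Ceiling: (1800 + 382 + 64)/2500 = 0.898. Then 2.0 shows as 1.90 and 1.5 as 1.45.
- With 40% aged 5–10: (1800 + 280 + 84)/2500 = 0.866, so 2.0 shows as 1.87.
- With 65% aged 5–10: (1800 + 455 + 49)/2500 = 0.922, so 2.0 shows as 1.92.

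**4. Group iii, if an arm-versus-arm ratio is calculated.** At 75% dosed overall, the dosed share outside the cohort is 1493/1800 = 0.83 (range 1420/1800 = 0.79 to 1595/1800 = 0.89). So 2.0 shows as 1.83 (1.79 to 1.89), or 2.0 if everyone in the group is dosed.

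**5. Drug-related events.** If only dosed people can have them, with risk p in dosed placebo recipients, the pooled ratio is (d × R × p)/(d × p) = R when dosed shares are equal. There is no dilution.

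**6. Unequal background risk.** Let k be recorded background risk in the undosed relative to the dosed:

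pooled RR = [dR + (1 − d)k] / [d + (1 − d)k]

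At d = 0.75 and R = 2.0:

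- k = 2: (1.5 + 0.5)/(0.75 + 0.5) = 1.60
- k = 3: (1.5 + 0.75)/(0.75 + 0.75) = 1.50
- k = 0.5: (1.5 + 0.125)/(0.75 + 0.125) = 1.86

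A k above 1 is plausible, because about half of the undosed (318 of 625) would be under-fives questioned weekly, but the documents give no value.

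**The case against.** **No specified analysis is wrong.** Group i is the randomised comparison, it matches protocol 10.1, and including the undosed is a deliberate choice. Receipt of tablets is determined after randomisation. All of this stands, and is why a dosed-set ratio can only be supplementary. A reader might infer that group i is the wrong safety analysis; the documents do not support that.

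**Group iii probably carries a ratio.** It is listed as a group under a sentence that sets relative risk as the measure, so an arm-versus-arm ratio is the natural reading. A reader might infer that people over 10 have no safety comparison apart from the all-enrolled one. That is too strong: the comparison is implied, left unstated, and only mildly diluted.

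**Drug-related AEs escape the dilution.** This stands. SAP 2.2.1 classifies AEs by relationship to the intervention, though it does not expressly state a ratio for each class. The concern is confined to all-cause AEs and SAEs, whose comparison does not depend on a causality judgement.

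**The 75% case is the less favourable one.** This stands too, so the ceiling figure belongs beside it. The assumption of no effect in the undosed is also a simplification, since the intervention is meant to act village-wide.

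**Wider ages mainly means children, whom ii.2 covers.** This is partly right, since IVERMAL treated adults. More frequent dosing still concerns every age.

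**Follow-up of transect households.** The Protocol Summary describes active AE monitoring "in a weekly visit and assessment of participants living in selected households located on our entomological sampling transects", and a reader might infer that the SAP contradicts the protocol by calling later non-cohort follow-up passive. Protocol 3.2.2 and 8.3 list no such visit, and Table 3 ("3 villages/arm; ~8 households/village") concerns blood sampling. The text supports only an inconsistency between the summary and the body, not a separate stratum.

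**Conclusion.** The gap is real and moderate. A placebo-controlled, all-cause AE or SAE risk ratio limited to people who took tablets is specified only for cohort children, leaving out about 80% of dosed people (76% to 85%). The one-arm guideline, the flow diagram and the small PK/PD cohort do not supply it.

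With equal background risk and no effect in the undosed, a true ratio of 2.0 shows in group i as 1.75 at 75% dosed and about 1.90 at the ever-dosed ceiling. An implied group iii ratio would show about 1.8 to 1.9, or 2.0 if all are dosed. These are illustrations resting on an assumed age spread, not estimates. Dilution is larger if recorded background risk is higher in the undosed and smaller if it is lower. The all-enrolled ratio remains the main safety comparison.

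**What to change.** In SAP 2.1.1 and 2.2.1:

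- Add a supplementary safety set: participants of any age with at least one study-team-observed dose of ivermectin or placebo.
- Compare all-cause AE and SAE risk by arm in that set, with allowance for village clustering, and report ACD-cohort and non-ACD participants separately because their follow-up differs.
- State the intervention-versus-control risk ratio for group iii.
- Report both beside the all-enrolled ratio, which stays the main comparison.
- Leave out a transect-household stratum unless the protocol body confirms weekly AE visits there.

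The cost is SAP wording and one or two table rows. No new data are needed: the study team gives the first daily dose of each round (protocol 2.2) and administration is recorded on the CRF (protocol 6.5). Days 2 and 3 are given by the caregiver, so the observed first dose should define the set. The downside is that receipt follows randomisation. The blinded placebo gives a like-for-like comparator, but does not make the dosed-set result a substitute for the randomised one.

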- Parasitological indices will provide a second-order mechanistic explanation of the intervention's effect on malaria incidence (the primary outcome): Prevalence, species and densities of asexual parasitemias will be scored from stain blood smears and analyzed over time and across arms, in both blood samples taken during the active case surveillance of cohort children, and in cross-sectional sampling of the whole study population. The genetic markers of parasites in participant dried blood spots will be analyzed for the multiplicity of infection, and the molecular force of infection over time. Samples will also be obtained at additional timepoints in a subset of participants, in order to obtain a baseline estimate for prevalence estimates. These finger prick blood samples will be collected during the dry seasons in 2020 and 2021, during the wet season in 2021 and at up to 4 other timepoints throughout the year. Baseline samples will allow for better assessment of changes occurring with IVM and SMC drug pressure. (This additional sampling will utilize a separate information sheet and consent document. Only participants who consent to participate in the additional sampling will do so.)
- Pharmacokinetics-dynamics will be studied in a sub-cohort of participants to link the presence of drug with mosquito biting and survival: Ivermectin in blood samples from different treated subjects (different age strata and genders) will be quantified and used to construct models to estimate and compare the pharmacokinetic parameters (e.g.  $C_{max}$ ,  $T_{1/2}$ ) across strata in blood. Entomology sampling in the houses of these participants following treatment will collect blood fed mosquitoes that will be 1) analyzed for survival, 2) tested for ivermectin in their blood meals, and 3) for the genetic signatures of the studied participants in the blood meal.

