- The *Plasmodium falciparum* multiplicity of infection per episode or blood sample, and number of new *Plasmodium falciparum* clones per unit time per child, will be significantly reduced in intervention arm children compared to control arm children.  
*Null: The Plasmodium falciparum multiplicity of infection per episode or blood sample, and number of new Plasmodium falciparum*

---

*clones per unit time per child, will not differ in intervention arm children compared to control arm children.*

- The concentration of ivermectin in participant's plasma will change over time post-drug administration and vary between age and gender strata. Mosquitoes that feed on recent ivermectin-treated participants will have detectable ivermectin in their blood meals. *Null: The concentration of ivermectin in participant's plasma will not change over time post-drug administration and will not vary between age and gender strata. Mosquitoes that feed on recent ivermectin-treated participants will not have detectable ivermectin in their blood meals.*

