- 6. Important medical events that may not result in death, be life-threatening, or require hospitalizations may be considered serious when, based upon appropriate medical judgment they may jeopardize the patient or subject and may require medical or surgical intervention to prevent one of the outcomes listed in this definition. Examples of such medical events include allergic reaction requiring intensive treatment in an emergency room or at home, blood dyscrasias or convulsions that do not result in inpatient hospitalization, or the development of drug dependency or drug abuse.

ii. Severity (grade)

- Grade 1 (mild)
- Grade 2 (moderate)
- Grade 3 (severe)
- Grade 4 (potentially life-threatening)
- Grade 5 (death)

iii. Outcome

- recovered/resolved without sequelae (grade for the event returned to <2)
- recovering/resolving (grade for event is decreasing and not greater than 2)
- not recovered/not resolving (adverse event still present but stable)
- recovered/resolved with sequelae (grade for the event returned to <2, however some pathological condition resulting from a disease, injury, or other trauma)
- Death
- unknown (example for using this code is when a participant is lost to follow up and outcome cannot be determined)
- iv. **By body system and preferred term** using MedDRA coding (27 groups)

2.2.2 Parasitological secondary endpoints and analysis.

The following are key secondary parasitological endpoints, and the method of analysis will depend on the type of data collected:

- Parasite prevalence. Parasite prevalence of *Plasmodium falciparum* will be assessed either by:
 - molecular assay (PCR-based off of filter paper from capillary finger-prick samples). Filter paper samples are obtained at the beginning and end of each intervention season, and monthly, prior to each MDA in the ACD cohort. In addition, filter paper was obtained in the entire cohort at the beginning and end of the 2020 intervention season.
 - blood smear (only for ACD children at the time of diagnosed malaria infection by RDT)
- Multiplicity of infection (MOI, also sometimes referred to as complexity of infection (COI). This is defined as the number of unique clones per individual at the time of diagnosis of malaria infection (count data). It is based either on microsatellite typing or amplicon sequencing

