- Molecular force of infection (mFOI; also sometimes further subclassified as molFOB (molecular force of blood stage infection). Defined as the number of new *Plasmodium* clones acquired over time (count data). Will be determined using monthly filter paper samples in ACD children only.

An approach consistent with the primary analysis will be adopted here with both unadjusted and adjusted regression models. For parasite prevalence, a binomial regression model will be used, and for MOI and mFOI, Poisson and Negative Binomial regression model will be used, with the final model choice being indicated by the distribution of the dependent variable.

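### SAP 2.2.2 takes smear prevalence and multiplicity of infection only at diagnosed malaria episodes, so neither is a randomised comparison of infection; PCR prevalence and mFOI are not affected

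*SAP*

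**What the plan says.** SAP 2.2.2 lists parasite prevalence, MOI and molecular force of infection (mFOI) as key secondary parasitological endpoints.

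- **Prevalence, PCR route.** Sampling follows a calendar and does not depend on diagnosis: "Filter paper samples are obtained at the beginning and end of each intervention season, and monthly, prior to each MDA in the ACD cohort". The whole cohort was also sampled at the start and end of the 2020 season.
- **Prevalence, smear route.** This is restricted: "blood smear (only for ACD children at the time of diagnosed malaria infection by RDT"). The two routes are offered as alternatives under one endpoint name, and one model covers both: "For parasite prevalence, a binomial regression model will be used".
- **MOI.** "This is defined as the number of unique clones per individual at the time of diagnosis of malaria infection (count data").
- **mFOI.** "Will be determined using monthly filter paper samples in ACD children only".
- **Count models.** "for MOI and mFOI, Poisson and Negative Binomial regression model will be used", with the choice between them guided by the observed distribution.

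SAP 2.1.2 defines a malaria episode as fever or recent fever plus a positive RDT for any species. Diagnosis is therefore the primary outcome event.

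The protocol is wider. Section 3.2.2 has smear prevalence scored "in both blood samples taken during the active case surveillance of cohort children, and in cross-sectional sampling of the whole study population". The blood-sampling schedule in section 4 (Table 3) has smears and filter papers from the child cohort before the season, between the second and third MDA, and after the season, as well as at diagnosis. Section 10.1 states the hypothesis for "multiplicity of infection per episode or blood sample". The SAP refers to MOI by sampling timepoint only in its appendix on future work.

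**The concern.** A prevalence needs a denominator that includes uninfected people. Children who are febrile and already RDT-positive are not such a group. If ivermectin lowers infection, fewer children enter the denominator, and those who do enter are still nearly all infected. Most of the effect disappears from the measure.

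MOI at diagnosis has a different problem. Ivermectin is meant to change who is diagnosed. The diagnosed children in the two arms are selected by the outcome and need not be alike in exposure or immunity. A difference, or the lack of one, can come from that selection.

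The protocol presents the parasitological indices as the second link in the mechanism behind the primary result. A flat smear result or a diluted MOI result could be read as evidence that infection did not fall.

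**Working it through.** **The plan's own figures.** The documents give no expected value, sample size or power for prevalence or MOI, so there is nothing to reproduce for these endpoints. The incidence rates borrowed below do reproduce. The rate ratio is 0.619/1.088 = 0.569, as in SAP 1.3. The standard formula for an unmatched cluster trial with a rate endpoint, with coefficient of variation 0.258 and 48 children per cluster, gives

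1 + (1.96 + 0.84)² × [(1.088 + 0.619)/48 + 0.258² × (1.088² + 0.619²)] / (1.088 − 0.619)² = 1 + 7.84 × 0.1399/0.2200 ≈ 5.99,

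which matches the stated 6 clusters per arm.

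**Smear positivity among RDT-positives.** Let p be infection prevalence among febrile children tested, Se and Sp the RDT sensitivity and specificity, and s the smear sensitivity. Smear specificity is taken as 1. Then

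P(smear+ | RDT+) = s × p·Se / [p·Se + (1 − p)(1 − Sp)].

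The factor s cancels from the arm ratio. None of these inputs is in the documents; they are assumptions. For a true halving of p, with s = 0.9:

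| p, control to intervention | Se | Sp | Control | Intervention | Ratio |
|---|---|---|---|---|---|
| 0.30 to 0.15 | 0.90 | 0.80 | 0.9 × 0.27/0.41 = 0.593 | 0.9 × 0.135/0.305 = 0.398 | 0.67 |
| 0.50 to 0.25 | 0.95 | 0.90 | 0.9 × 0.475/0.525 = 0.814 | 0.9 × 0.2375/0.3125 = 0.684 | 0.84 |
| 0.70 to 0.35 | 0.95 | 0.95 | 0.9 × 0.665/0.680 = 0.880 | 0.9 × 0.3325/0.365 = 0.820 | 0.93 |

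The true ratio is 0.50 in every row. For a true ratio of 0.569 and similar inputs, the measure gives 0.73 to 0.95. If Sp were 1, the ratio would be exactly 1. Any signal that remains is therefore carried by RDT false positives.

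**Who contributes to MOI at diagnosis.** With 7 × 100 = 700 children per arm (SAP 1.3):

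- Episodes per arm-year: 700 × 1.088 ≈ 762 in control and 700 × 0.619 ≈ 433 in intervention.
- Children with at least one episode, under a Poisson assumption without heterogeneity: 1 − e^(−1.088) = 66% and 1 − e^(−0.619) = 46%.

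**Direction of the selection.** In a simulation, exposure varied between children (gamma, shape 0.5 to 2, control mean 2 clones), the chance of diagnosis rose with exposure, and treatment multiplied exposure by 0.569. Diagnosed intervention children had higher underlying exposure than diagnosed controls in every setting, for example 1.64 against 1.50 relative to a cohort mean of 1. The MOI ratio among the diagnosed was 0.68 to 0.72, against 0.569 for the exposure ratio. That gap combines selection with the absence of zero counts.

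**Fit of the count model.** Suppose clone counts are Poisson before the zeros are removed, with control mean L and a true ratio of 0.569. The observed ratio is then 0.83 at L = 1, 0.72 at L = 2, 0.66 at L = 3 and 0.60 at L = 5. The control variance-to-mean ratio is 0.42, 0.69, 0.84 and 0.97. Simulated type I error of a plain Poisson test (400 samples per arm, no clustering) was 0.0%, 1.9% and 2.9% at L = 1, 2 and 3, which is conservative. With overdispersed counts the variance misfit can vanish. The documents give neither mean MOI nor its dispersion.

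**The case against.** The strongest reply is that the plan already measures infection properly. PCR prevalence uses scheduled filter papers and mFOI uses monthly ones; neither depends on diagnosis, and together they carry the infection comparison. This stands. It limits the point to the smear route and to MOI.

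Second, the protocol does not forbid MOI at episodes. Section 10.1 joins the two sampling bases with an or, and the objective in section 3.1.2 speaks of samples taken during active case surveillance. This also stands: for MOI the SAP narrows the protocol and does not flatly contradict it. It has nevertheless kept the selected version as a key secondary endpoint and left the timepoint version to future work.

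Third, mean clones per diagnosed child is a legitimate description, and a log-link Poisson model without covariates or random effects returns the ratio of observed means exactly. That is true. The objection is to reading that ratio as a treatment effect on infection.

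Three stronger readings are tempting, and the documents do not support them:

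- A reader might infer that smear positivity would be flat whatever ivermectin does. The working shows attenuation, not constancy.
- A reader might infer that MOI at diagnosis can never be zero. The RDT criterion accepts any species while the MOI hypothesis concerns *P. falciparum*, and false positives occur, so zeros are possible. The real gap is that the SAP does not say how to count them.
- A reader might infer that the planned count model is simply wrong, and back-calculate a larger effect through a truncated model. That needs mean MOI values that the documents do not give, and it replaces the stated endpoint with a latent clone rate.

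**Conclusion.** The point holds for two measures in SAP 2.2.2. The smear route is slide confirmation of the RDT and would understate an arm difference: a ratio of about 0.67 to 0.93 for a true halving, under the assumed test accuracy and infection prevalence. MOI at diagnosis compares children selected by the primary outcome, about 66% against 46% of each arm per year at the planned rates. Randomisation does not protect it. The size of the resulting bias depends on heterogeneity in exposure that the documents do not describe.

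PCR prevalence, mFOI and the primary analysis are unaffected. Misfit of the Poisson or negative binomial model is a secondary matter: it ranges from marked at a mean MOI of 1 to 2 to slight near 5, and under pure truncation it errs on the conservative side.

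**What to change.** 1. Base the prevalence comparison on the scheduled PCR samples, with every sampled child in the denominator. Add scheduled cross-sectional smears only if they were taken: the protocol schedules them, but the SAP mentions only filter papers at those times.
2. Rename the episode smear result as slide confirmation, or parasite density among episodes.
3. Make MOI on the scheduled monthly filter papers the between-arm comparison, and keep the village random effect.
4. Report MOI at episodes as descriptive, and say how repeat episodes in one child are handled.
5. State whether samples without falciparum clones count as zero or as missing. On the scheduled samples, counting them as zero keeps all sampled children in the comparison.
6. A zero-truncated or hurdle model may be added as a sensitivity analysis; it is optional.
7. Reconcile SAP 2.2.2 and the SAP appendix with protocol sections 3.2.2, 4 and 10.1.

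The cost is SAP wording. No new sampling or smear reading is needed, and little or no extra laboratory work should follow, because mFOI already requires clone typing of the monthly cohort filter papers.
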